6.6.1.3 Combination therapy pasireotide LAR and everolimus

Patients assigned to this treatment arm will be given a combination therapy based on pasireotide LAR 60 mg i.m. and everolimus 10 mg p.o. q.d. as described for each study drug above.

6.6.2 Study drug packaging and labeling

Medication labels will be in the local language and comply with the legal requirements of each country. They will include storage conditions for the drug but no information about the patient.

6.6.3 Drug supply and storage

Study drugs must be received by a designated person at the study site, handled and stored safely and properly, and kept in a secured location to which only the investigator and designated assistants have access. Upon receipt, pasireotide LAR and everolimus should be stored according to the instructions specified on the drug labels. Clinical supplies are to be dispensed only in accordance with the protocol. Details are listed in [Table 6-14](#).

Table 6-14 Supply and storage of study treatments

Study treatments	Supply	Storage
Pasireotide LAR	Centrally supplied by Novartis	Refer to study treatment label
Everolimus	Centrally supplied by Novartis, or by local commercial stock, once available	Refer to study treatment label

6.6.3.1 Pasireotide LAR

Study drug pasireotide LAR i.m. depot injections will be supplied in open-label packaging by Novartis as a powder in vials containing 20 mg, 40 mg and 60 mg, with ampules containing 2 mL of vehicle (for reconstitution). No syringes or needles will be provided with the pasireotide study drug supplies.

6.6.3.2 Everolimus

Study drug everolimus will be supplied in open-label packaging by Novartis (centrally or by local commercial stock, once available) as tablets of either 10 mg or 5 mg strength, blister-packed under aluminium foil in units of 10 tablets and dosed on a daily basis. Everolimus tablets should be opened only at the time of administration as the drug is both hygroscopic and light-sensitive.

6.6.4 Study drug compliance and accountability

6.6.4.1 Study drug compliance for everolimus

Compliance will be assessed by the investigator and/or study personnel at each visit using tablet counts. Records of study medication used, treatment administered, and intervals between visits will be kept during the study. This information should be captured in the source document at each patient visit.

- Patients will be requested to bring their unused medication including empty packaging to the clinic at each visit, at the end of the study and at the time of study treatment discontinuation.
- All doses taken by the patient and all dose changes during the study must be recorded on the CRF.

6.6.4.2 Study drug accountability

The investigator or designee must maintain an accurate record of the shipment and dispensing of study treatment in a drug accountability ledger (overall drug accountability log for the study as well as individual study drug accountability records for each patient) of tablets administered, tablets used, dose changes, dates dispensed and intervals between visits. Drug accountability will be noted by the field monitor during site visits and at the completion of the study.

At study close-out, and, as appropriate during the course of the study, the investigator will return all used and unused study treatment, packaging, drug labels, and a copy of the completed drug accountability ledger to the Novartis monitor or to the Novartis address provided in the investigator folder at each site.

6.6.5 Disposal and destruction

The drug supply can be destroyed at the local Novartis facility, Drug Supply group or third party, as appropriate. Study drug destruction at the investigational site will only be permitted if authorized by Novartis in a prior agreement and if permitted by local regulations.

7 Visit schedule and assessments

7.1 Study flow and visit schedule

Table 7-1 lists all of the assessments and indicates with an “X” the visits when they are performed. All data obtained from these assessments must be supported in the patient’s source documentation. The table indicates which assessments produce data to be entered into the database (D) or remain in source documents only (S) (“Category column”).

[figure not shown]
[figure not shown]

Table 7-1 CORE STUDY – Visit evaluation schedule (12 months)

Visit Name	Category	Reference to Section 7.2	Screening Baseline	Core study																	End of core study/Early withdraw (EOS)	Safety FU visit **
				1	2	3	4	5	6	7	8	9	10	11	12	13	14	15	16	17		
Study Day			-28 to-1	1	15	21	29	49	57	85	113	141	169	197	225	253	281	309	337			
Week				2	3	4	7	8	12	16	20	24	28	32	36	40	44	48	52			
Obtain Informed Consent	D		X																			
Patient history	D		X																			
Demography	D		X																			
Relevant medical history/current medical conditions incl. cancer-related conditions and symptoms	D		X																			
Diagnosis and extent of cancer	D		X																			
Prior antineoplastic therapies, therapy for lung/thymus NET	D		X																			
Inclusion/exclusion criteria	S		X																			
Prior/concomitant medications	D		X	X	X	X	X	X	X	X	X	X	X	X	X	X	X	X	X	X	X	X
Physical examination	S	7.2.2.1	X	X	X		X		X	X	X	X	X	X	X	X	X	X	X	X	X	

Visit Name	Category	Reference to Section 7.2	Screening Baseline	Core study																	End of core study/Early withdraw (EOS)	Safety FU visit **
				1	2	3	4	5	6	7	8	9	10	11	12	13	14	15	16	17		
Study Day			-28 to-1	1	15	21	29	49	57	85	113	141	169	197	225	253	281	309	337			
Week				2	3	4	7	8	12	16	20	24	28	32	36	40	44	48	52			
WHO Performance status	D	7.2.2.4	X	X	X		X		X	X	X	X	X	X	X	X	X	X	X	X		
Height	D	7.2.2.3	X																			
Weight	D	7.2.2.3	X	X	X		X		X	X	X	X	X	X	X	X	X	X	X	X		
Vital signs	D	7.2.2.2	X	X	X		X		X	X	X	X	X	X	X	X	X	X	X	X		
Chest X-ray, or chest CT scan	D	7.2.2.6.1	As medically indicated																			
Hepatitis screening (HBV-DNA, HBsAg, HBsAb, HbCAb, HCV RNA-PCR)	D	7.2.2.5.10	X																			
Monitoring for HBV-DNA, HCV RNA-PCR every 4 weeks (if applicable)	D	7.2.2.5.10					X		X	X	X	X	X	X	X	X	X	X	X	X		
Anti-HAV, IgM, HbsAg, Anti-HBc, anti-HCV (if positive, PCR viral load should be assessed), Anti-HEV, ANA antibodies, anti-smooth muscle antibodies, CMV and	D			If LFTs meet criteria reported in Section 6.1.5																		

Visit Name	Category	Reference to Section 7.2	Screening Baseline	Core study																		End of core study/Early withdraw (EOS)	Safety FU visit **
				1	2	3	4	5	6	7	8	9	10	11	12	13	14	15	16	17	18		
Study Day			-28 to-1	1	15	21	29	49	57	85	113	141	169	197	225	253	281	309	337				
Week				2	3	4	7	8	12	16	20	24	28	32	36	40	44	48	52				
EBV																							
Laboratory evaluations		7.2.2.5																					
Hematology	D	7.2.2.5.1	X	X	X		X		X	X	X	X	X	X	X	X	X	X	X				
Coagulation (INR)	D	7.2.2.5.2	X	X		X*	X	X*	X	X		X		X		X		X					
Coagulation (PTT)		7.2.2.5.2	X																				
Biochemistry	D	7.2.2.5.3	X	X	X		X		X	X	X	X	X	X	X	X	X	X	X				
Fasting glucose/insulin/HbA1c (everolimus monotherapy)	D	7.2.2.5.4	X	X	X	X	X	If medically indicated	X	X	X	X	X	X	X	X	X	X	X				
Fasting glucose/insulin/HbA1c (combination)	D	7.2.2.5.4	X	X	X	X	X	X	X	X	X	X	X	X	X	X	X	X	X				
Fasting glucose/insulin/HbA1c pasireotide LAR monotherapy	D	7.2.2.5.4	X	X	X	X	X	X	X	X	X	X	X	X	X	X	X	X	X				
Blood glucose self monitoring (if applicable)		7.2.2.5.4	Continuous																				
Liver Function Tests	D	7.2.2.5.5	X	X	X	X*	X	X*	X	X	X	X	X	X	X	X	X	X	X				

Visit Name	Category	Reference to Section 7.2	Screening Baseline	Core study																		End of core study/Early withdraw (EOS)	Safety FU visit **
				1	2	3	4	5	6	7	8	9	10	11	12	13	14	15	16	17	18		
Study Day			-28 to-1	1	15	21	29	49	57	85	113	141	169	197	225	253	281	309	337				
Week				2	3	4	7	8	12	16	20	24	28	32	36	40	44	48	52				
ACTH	D	7.2.2.5.3	X	Every 3 months, if ACTH hypersecretion at baseline																			
Serum lipid profile	D	7.2.2.5.6	X	X		X			X	X	X	X	X	X	X	X	X	X	X	X			
Thyroid function test	D	7.2.2.5.7	X							X			X							X			
Urinalysis	D	7.2.2.5.8	X	X	X		X		X	X	X	X	X	X	X	X	X	X	X	X			
Pregnancy test	D	7.2.2.5.9	X	X			X		X	X	X	X	X	X	X	X	X	X	X	X			
CgA and 5HIAA	D	7.2.1.2	X							X			X			X			X	X			
Imaging/Other assessments																							
Tumor evaluation	D	7.2.1.1	X							X			X			X			X	X			
Gallbladder assessment	D	7.2.2.6.4	X							X*			X*			X*			X*	X*			
Pulmonary Function Test	D	7.2.2.6.2	As medically indicated																				
Bronchoscopy	D	7.2.2.6.3	As medically indicated																				
ECG	D	7.2.2.7.1	X	X		X				X		X			X			X		X			
Cardiac imaging (ECHO or MUGA scan)	D	7.2.2.7.2	X	As medically indicated																			
Safety																							
Adverse events	D			X	X	X	X	X		X	X	X	X	X	X	X	X	X	X	X	X		X

Visit Name	Category	Reference to Section 7.2	Screening Baseline	Core study																	End of core study/Early withdraw (EOS)	Safety FU visit **
				1	2	3	4	5	6	7	8	9	10	11	12	13	14	15	16	17		
Study Day			-28 to-1	1	15	21	29	49	57	85	113	141	169	197	225	253	281	309	337			
Week				2	3	4	7	8	12	16	20	24	28	32	36	40	44	48	52			
Contact IVRS for randomization			X																			
Pasireotide LAR injections (q28d)	D			X			X		X	X	X	X	X	X	X	X	X	X	X	X	X	X***
Everolimus administration (daily)	D			Daily***																		
Core study completion	D																				X	
*Only for patients treated with pasireotide LAR ** The safety FU visit should be performed only for patients who prematurely discontinue study treatment or experience disease progression at week 52. The visit should be performed 56 days after the last dose of pasireotide LAR or everolimus, whichever comes last. ***Pasireotide LAR injection and everolimus should be given at V18 only to patients that continue the extension phase																						

[figure not shown]
[figure not shown]

Table 7-2 EXTENSION PHASE - Visit evaluation schedule

Visit No.	Category	Reference to Section 7.2	Extension phase					End of extension phase /Early withdrawn	Safety FU visit**
			1	2	3	4			
Month of extension phase			3	6	9	12	Every 3 mos		
Vital signs	D	7.2.2.2	X	X	X	X	X	X	
Physical examination	S	7.2.2.1	X	X	X	X	X	X	
Weight	D	7.2.2.3	X	X	X	X	X	X	
WHO performance status	D	7.2.2.4	X	X	X	X	X	X	
Tumor evaluation, frequency at investigator's discretion***	D	7.2.1.1	X	X	X	X	X	X	
Gallbladder assessment, frequency as per tumor evaluation at investigator's discretion	D	7.2.2.6.4	X*	X*	X*	X*	X*	X*	
Pulmonary Function Test	D	7.2.2.6.2	As medically indicated						
Bronchoscopy	D	7.2.2.6.3	As medically indicated						
Chest X-ray, or Chest CT scan	D	7.2.2.6.1	As medically indicated						
ECG	D	7.2.2.7.1	X	X	X	X	X	X	
Cardiac imaging (ECHO or MUGA scan)	D	7.2.2.7.2	As medically indicated						
Hematology	D	7.2.2.5.1	X	X	X	X	X	X	
Biochemistry	D	7.2.2.5.3	X	X	X	X	X	X	
Fasting glucose/insulin/HbA1c (everolimus monotherapy)	D	7.2.2.5.4	X	X	X	X	X	X	
Fasting glucose/insulin/HbA1c (combination)	D	7.2.2.5.4	X	X	X	X	X	X	
Fasting glucose/insulin/HbA1c pasireotide LAR monotherapy	D	7.2.2.5.4	X	X	X	X	X	X	
Blood glucose self monitoring (if applicable)		7.2.2.5.4	Continuous						
Liver Function Tests	D	7.2.2.5.5	X	X	X	X	X	X	

[figure not shown]
Visit No.	Category	Reference to Section 7.2	Extension phase					End of extension phase /Early withdrawn	Safety FU visit**
			1	2	3	4	Every 3 mos		
Month of extension phase			3	6	9	12	Every 3 mos		
Coagulation (INR)	D	7.2.2.5.2	X	X	X	X	X	X	
CgA and 5HIAA****	D	7.2.1.2		X		X			
Urinalysis	D	7.2.2.5.8	X	X	X	X	X	X	
Serum lipid profile	D	7.2.2.5.6	X	X	X	X	X	X	
Pregnancy test	D	7.2.2.5.9	X	X	X	X	X	X	
Monitoring of HBV-DNA, HCV RNA-PCR (if applicable)	D		Every 4 weeks as indicated in Section 6.1.4.8						
Anti-HAV, IgM, HbsAg, Anti-HBc, anti-HCV (if positive, PCR viral load should be assessed), Anti-HEV, ANA antibodies, anti-smooth muscle antibodies, CMV and EBV	D		If LFTs meet criteria reported in Section 6.1.5						
Pasireotide LAR injections (q28d)	D		Every 28 days from V18 of Core phase						
Everolimus administration (daily)	D		Daily from V18 of Core phase						
Adverse events	D		X	X	X	X	X	X	X
Concomitant medications	D		X	X	X	X	X	X	X
Study completion	D							X	

*Only for patients treated with pasireotide LAR

**The safety follow up visit should be performed 56 days after the last dose of pasireotide LAR or everolimus, whichever comes last.

*** Patients who discontinue study treatment after 12 months of treatment without evidence of progression or for reasons other than disease progression will continue to have tumor evaluation assessments until disease progression or last patient last visit (LPLV) whichever occurs first.

**** CgA and 5HIAA will only be collected until extension visit 4.

7.1.1 Pre-screening assessments

Not applicable.

7.1.2 Screening

7.1.2.1 Eligibility screening

The principal investigator is responsible for patient's eligibility.

7.1.2.2 Information to be collected on screening failures

Patients who complete the informed consent process and do not meet all entry criteria and therefore who do not receive first dose of study drug(s) will be considered screen failures. For screening failure patients, no data will be entered in the clinical database, except for the reasons of screening failure.

7.1.2.3 Patient demographics and other baseline characteristics

[figure not shown]
Patient demographics and baseline characteristics will include the following: demography, medical history/current medical conditions (including cancer-related conditions and symptoms), diagnosis and extent of cancer, prior anticancer therapies taken, disease-related symptoms, prior/concomitant medication taken, physical examination, WHO performance status, vital signs, weight and height, hepatitis B and C screening, hematology, blood chemistry, coagulation panel, urinalysis, pregnancy test required for women of childbearing potential, ECG.

7.1.3 Treatment period

This study has a treatment duration of 12 months (core study). Patients will either start pasireotide LAR or everolimus treatment or a combined treatment of both pasireotide LAR and everolimus regimens at visit 2.

7.1.4 End of core study visit, including premature withdrawal and study discontinuation visit

Patients who discontinue study treatment should be scheduled for a visit as soon as possible, at which time all of the assessments listed for the end of core study visit/early withdrawn will be performed. Study treatment discontinuation in the pasireotide LAR plus everolimus arm is defined as the withdrawal of both study drugs; the date and reason for stopping the study treatment should be reported in the CRF. At a minimum, all patients who discontinue study treatment, including those who refuse to return for a final visit, will be contacted for safety evaluations 56 days after the last dose of pasireotide LAR or everolimus, whichever comes last.

7.1.4.1 Criteria for premature patient withdrawal

Patients **may** voluntarily withdraw from the study or be dropped from it at the discretion of the investigator at any time. Patients may be withdrawn from the study if any of the following occur:

1. Disease progression
2. Unacceptable toxicity / adverse events which are not listed below
3. Clinically significant abnormal lab values
4. Clinically significant abnormal test procedure results
5. Protocol violation
6. Administrative problems
7. Pregnancy
8. Patient withdrawing informed consent
9. New anticancer therapy
10. Patient lost to follow-up
11. Death

In addition to the general withdrawal criteria, the following **study specific criteria** will also require study treatment discontinuation:

1. Patients experiencing unacceptable toxicity as described in [Table 6-1](#), [Table 6-2](#), [Table 6-4](#), [Table 6-5](#), [Table 6-6](#) and [Table 6-7](#).
2. Patient with blood glucose values consistently in excess of 250 mg/dL persisting after interruption of study drug in spite of continuous, appropriate therapeutic intervention(s).
3. Confirmed QTcF >470 msec and discontinuation recommended by a cardiologist after examination of cardiovascular risk factors.
4. Mean QTcF >500 msec measured by triplicate ECGs, and discontinuation recommended by a cardiologist, after ECG re-evaluation and confirmation of a mean QTcF value >500 msec.
5. Significant arrhythmia findings from Holter monitoring such as:
 - Any ventricular or supra-ventricular tachyarrhythmia associated with symptoms of hemodynamic compromise
 - Sustained ventricular tachycardia (>30 sec) irrespective of symptoms
 - Recurrent non-sustained VT (≥ 3 beats) during any 24-hour monitoring period
 - Torsades de Pointes (TdP)
 - Cardiac arrest
 - Pause >5 seconds
 - Second or third degree AV block.
6. New occurrence of clinically significant/symptomatic bradycardia.
7. Increased risk of QT prolongation by use of QT prolonging medication.
8. Hypokalemia (<3.5 mmol/L) or hypomagnesaemia (<0.7 mmol/L or below the LNR as provided by the laboratory) confirmed by repeat testing that is either a new finding or accompanied by vomiting or diarrhea and not corrected by treatment.

9. Abnormal Liver Function Tests such as:

- ALT or AST > 3 x ULN and Total Bilirubin \geq 2 x ULN and ALP < 2 x ULN;
- ALT or AST > 5 x ULN and \leq 8 x ULN persistent for more than 2 weeks;
- ALT or AST > 8 x ULN.

If such withdrawal occurs, or if the patient fails to return for visits, the investigator must determine the primary reason for a patient's premature withdrawal from the study and record this information on the CRF.

All patients who discontinue study treatment must have safety evaluations 56 days after the last dose of pasireotide LAR or everolimus, whichever comes last.

All cancer medications/therapies given to a patient up to 56 days after the last dose of study treatment must be recorded in the CRF.

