6.1 Investigational treatment, other study treatment, supportive treatment

The investigational study drugs used in the course of this trial are pasireotide (SOM230) LAR and everolimus (RAD001). For the duration of the trial, pasireotide LAR and everolimus will be supplied by Novartis, or by local commercial stock, once available.

Therefore, if at any time during the study life pasireotide LAR and/or everolimus become commercially available in the Countries participating to the study the local commercial stock should be used.

Definition of terms:

- Study drug = pasireotide (SOM230) LAR or everolimus (RAD001)
- Study treatment = pasireotide (SOM230) LAR or everolimus (RAD001) alone or a combination of pasireotide LAR and everolimus.

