6.1.4.9 Management of ECG changes

SSAs have shown an influence on cardiac signal transduction.

Pasireotide administered subcutaneously has been shown to prolong the QT interval in healthy subjects based on two Phase I studies [[CSOM230B2113](#)] and [[CSOM230B2125](#)]. Additional analysis of thorough QT study data [[CSOM230B2125](#)], including quantitative ECG beat to beat restitution analysis, showed that pasireotide does not alter cardiac repolarization in the same manner as drugs known to prolong QT that are associated with pro-arrhythmia.

In clinical studies in Cushing's disease patients, QTcF of >500 msec was observed in two out of 201 patients. These episodes were sporadic and of single occurrence with no clinical consequence observed.

Episodes of torsade de pointes were not observed in any clinical study with pasireotide.

If at any visit a QTcF > 500 msec is observed, triplicate ECGs, each 2-3 minutes apart, need to be taken approximately 1 hour after the initial ECG. The mean QTcF from the triplicate ECGs will be determined. If the mean QTcF is > 500msec, the patient will need to be closely monitored at the hospital and will have to postpone pasireotide LAR treatment until a cardiologist has re-evaluated the ECG (this can be done by the central cardiologist if the trial has one). If the cardiologist confirms a mean QTcF >500 msec, the patient has to discontinue. Otherwise and if the cardiologist confirms that at least one ECG shows a QTcF > 470msec, the cardiac assessments described for a confirmed QTcF > 470msec need to be followed (see [Figure 6-1](#)).

If at any visit a $470 \text{ msec} < \text{QTcF/mean QTcF} \leq 500\text{msec}$ is observed, the following steps need to be taken (refer to [Figure 6-1](#)):

[figure not shown]
- postpone pasireotide LAR administration;
- a cardiology consultation must be sought as soon as practical but within 7 days of the initial abnormal ECG and the cardiologist must re-evaluate the ECG (this can be done by the central cardiologist if the trial has one).
 - If a QTcF > 470msec is NOT confirmed, no further action needs to be taken, and pasireotide LAR can be restarted.
 - If a QTcF > 470msec is confirmed, a cardiologist must perform a thorough examination (such as reviewing baseline ECG, concurrent medications and performing a cardiovascular examination, including at least a cardiac auscultation) to assess the patient for cardiovascular risk factors.

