 - If based upon the assessment by the cardiologist, the investigator considers that there is an acute cardiovascular safety risk and that the patient should not continue with study medication, the patient needs to be discontinued immediately (discontinuation criteria to be followed).
 - If following the examination by the cardiologist, the investigator considers that there is not an acute cardiovascular safety risk and that the patient could restart to receive study medication, a Holter ECG (24hr or 48hr depending on the study) must be recorded soon as practical but within 7 days after the initial abnormal ECG / at the next pasireotide LAR injection. The Holter-ECG must be started 30min prior to an injection of study medication.

The results of the ECGs, cardiac examination, Holter-ECGs and the recommendation by the cardiologist must be evaluated by the investigator to determine whether the patient should continue the trial or not (discontinuation criteria to be followed).

Overall, the monitoring of ECG changes has to be performed in all patients, irrespective of the treatment arm they have been assigned to (thus, not only in patients taking everolimus alone or in combination, but also in patients on pasireotide alone), taking into account the observed QTcF value. However, in light of evidence that the risk for ECG changes is related to SSA

treatment, the drug interruption/discontinuation strategy (see Figure 6-1) will apply to pasireotide LAR only.

Figure 6-1 Procedure for QTcF prolongations

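### Protocol 7.1.4.1 item 4 adds a cardiologist's recommendation to a stop that 6.1.4.9 makes mandatory once a mean QTcF above 500 msec is confirmed

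*Protocol*

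**What the plan says.** Two parts of the protocol state what happens when the mean QTcF on triplicate ECGs exceeds 500 msec.

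- **Section 6.1.4.9 (Management of ECG changes).** After a single QTcF above 500 msec at any visit, triplicate ECGs are taken. If their mean is also above 500 msec, the patient is monitored closely in hospital and pasireotide LAR is postponed until a cardiologist has looked at the ECG again. Then: "If the cardiologist confirms a mean QTcF >500 msec, the patient has to discontinue". If the mean is not confirmed but at least one ECG exceeds 470 msec, the steps for the 470 to 500 msec range apply.
- **Section 7.1.4.1 (Criteria for premature patient withdrawal), item 4.** The criterion is "Mean QTcF >500 msec measured by triplicate ECGs, and discontinuation recommended by a cardiologist", followed by "after ECG re-evaluation and confirmation of a mean QTcF value >500 msec". It is one of the study-specific criteria that "will also require study treatment discontinuation".

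Section 7.1.4.1 is the list that Sections 4.1.3, 4.4 and 7.1.5 name when they set out how long a patient may remain on treatment in the extension phase.

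**The concern.** The same clinical finding has two different stopping conditions. In 6.1.4.9 the cardiologist's task above 500 msec is to confirm or refute the measurement; confirmation settles the matter. In item 4 the cardiologist must confirm the measurement and also recommend stopping. A stop that is automatic in one section depends on judgement in the other.

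What is at stake is safety conduct. The looser wording is in the list that sites are told to use when deciding whether an extension-phase patient may continue. In that phase Table 7-2 schedules ECGs every 3 months and pasireotide LAR injections every 28 days. A site that goes by the list alone could give further injections to a patient who has to discontinue under 6.1.4.9.

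**Working it through.** The main check is a comparison of text; no sample size, power or error rate is involved.

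**Step 1: compare the two rules.** Take a patient on pasireotide LAR whose triplicate mean QTcF exceeds 500 msec.

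| Cardiologist confirms the mean | Cardiologist recommends stopping | Section 6.1.4.9 | Item 4 of 7.1.4.1 |
|---|---|---|---|
| Yes | Yes | Stop | Stop |
| Yes | No | Stop | Not met |
| No | Either | No stop under the 500 msec rule; 470 msec steps if at least one ECG exceeds 470 msec | Not met |

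Only the second row differs.

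**Step 2: is the recommendation a real extra condition?** Item 4 names the recommendation and the confirmation separately, so the first is not simply another word for the second.

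**Step 3: does the rest of the protocol show which version is intended?** Three features favour 6.1.4.9.

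- A confirmed mean above 500 msec is also above 470 msec. Item 3 already requires a stop for a confirmed QTcF above 470 msec when a cardiologist recommends it after examining risk factors. With the recommendation included, item 4 adds almost nothing to item 3. Without it, item 4 has a clear purpose.
- Section 6.1.4.9 has two tiers: judgement from 470 to 500 msec, and an automatic stop at a confirmed mean above 500 msec. Item 4 makes the upper tier depend on judgement too.
- Elsewhere the list repeats Section 6 faithfully: the liver limits in item 9 match Section 6.3.2.1. The Amendment 4 log, used here only as evidence of intent, says that the QTcF details in Section 7.1 were set to follow 6.1.4.9.

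**Step 4: how many patients could be affected?** The inputs are in the Amendment 5 rationale: 124 randomized, 41 entered the extension phase, 30 of those had discontinued.

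- Still on treatment: 41 − 30 = 11, which agrees with the 11 stated.
- Share of those randomized: 11 / 124 = 8.9%.
- Split by arm: not given, so between 0 and 11 were on pasireotide LAR, alone or in combination.

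**Step 5: how rare is the trigger?** Section 6.1.4.9 reports QTcF above 500 msec in 2 of 201 patients with Cushing's disease, 2 / 201 = 1.0%, as sporadic single readings without clinical consequence. If that proportion applied here and all 11 patients were on pasireotide LAR, the expected number would be 11 × 2 / 201 = 0.11 patients. This is only an illustration: the population differs, and those readings are not described as triplicate means or as confirmed by a cardiologist. The second row of the table would be rarer still.

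**The case against.** The strongest reply is that the sections do not contradict each other. Item 4 gives one set of circumstances in which treatment must stop; it nowhere says that a patient with a confirmed mean above 500 msec may continue. The list is introduced as an addition to the general criteria and does not claim to be complete or to override 6.1.4.9, which applies at any visit and so in the extension phase as well. The triplicate procedure that item 4 presupposes is set out in 6.1.4.9, so a site carrying it out should have that section open. The general criteria in 7.1.4.1 also allow withdrawal for "Clinically significant abnormal test procedure results". On this view item 4 is a loose summary.

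Much of this stands. A reader might infer that the protocol permits treatment after a confirmed mean above 500 msec; it does not, because 6.1.4.9 still binds. What remains is that the mandatory list omits a mandatory stop. The general criteria do not close that gap, because they say only that a patient may be withdrawn.

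Two further inferences are tempting and should not be drawn.

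- **That 6.1.4.9 itself sends a confirmed case above 500 msec to item 4.** Its closing instruction is to weigh the findings "to determine whether the patient should continue the trial or not (discontinuation criteria to be followed". That sentence, and the similar phrase before it, follow the steps for 470 to 500 msec and refer to Holter recordings ordered only on that path. The path for a confirmed mean above 500 msec ends with discontinuation.
- **That items 3 and 4 need an arm limit.** They name no arm, and Section 6.1 defines "Study treatment = pasireotide (SOM230) LAR or everolimus (RAD001) alone or a combination of pasireotide LAR and everolimus". Read literally, they stop an everolimus-monotherapy patient whom a cardiologist advises to stop, although 6.1.4.9 says "the drug interruption/discontinuation strategy (see Figure 6-1) will apply to pasireotide LAR only". The difference in wording is real, but 6.1.4.9 already states the limit. The literal reading gives the more cautious result, and an arm limit would turn a required stop into a discretionary one. Which text ought to change would also depend on Figure 6-1, which is not shown in this copy. The combination arm is unaffected, because under Section 6.3.2 stopping one drug stops both.

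**Conclusion.** The point holds: item 4 of 7.1.4.1 is narrower than the mandatory stop in 6.1.4.9, because it adds a recommendation that 6.1.4.9 does not require. Harm would need two things together: a cardiologist who confirms a mean above 500 msec without recommending discontinuation, and a site that consults only the list.

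It is minor. At most 11 patients could still be exposed at Amendment 5, fewer if some were on everolimus alone, and the documents report no such case. Because Section 10.4.3 counts discontinuation before Month 9 as not progression-free, a reader might infer an effect on the primary endpoint. The documents do not support that: the primary analysis was performed on 26 February 2016, before this protocol version was released on 7 November 2016, and no affected patient is described.

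The conclusion assumes that Figure 6-1 agrees with the text of 6.1.4.9 on the confirmed mean above 500 msec.

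**What to change.** Reword item 4 so that confirmation alone is enough: triplicate mean QTcF above 500 msec, confirmed by a cardiologist on re-evaluation of the ECG (see Section 6.1.4.9). Leave item 3 unchanged and add no arm limit to either item. Check Figure 6-1 for agreement before finalising.

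The edit is one clause, but Section 12.1 requires any protocol change to be a written amendment approved by the sponsor, the ethics bodies and, where required, health authorities. Sites should be notified. No analysis changes: SAP Section 10.8 tabulates QTcF and does not use the stopping rule.

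One side effect should be accepted knowingly. Read without 6.1.4.9, the shorter item 4 would also require a stop in everolimus monotherapy at a confirmed mean above 500 msec. That errs towards caution, and the cross-reference leads the reader to the sentence that limits the strategy to pasireotide LAR.
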